Appendix

Initial Questionnaire
Clinical Evaluation Criteria

INITIAL QUESTIONNAIRE

Pati	ent: Date:
1.]	Birthdate (month-day-year)
2. (Gender:male female
	Caries Risk Assessment Low 0-1 carious lesions in the last 24 months Moderate 2-4 carious lesions in the last 24 month High 4+ carious lesions in the last 24 month (disqualifies)
	Teeth to be restored Anterior abutment: Posterior abutment:
	Pre-operative vitality; verify with cold test: Abutment tooth: Vital Devital (circle one) Abutment tooth: Vital Devital (circle one)
6.	Verify pre-operative PAXR for test teeth; less than 6 months old (initials)
7.	Occlusion – at least one centric stop per tooth (initials)
	lateral guidance location:
8.	Informed Consent and HIPPA form signed (initials)
9.	Pre-operative Shade: (photograph shade tab/s with control tooth) shade details:
10.	Opposing Tooth: (photograph opposing teeth; with and without occlusal contacts marked
	Restorative material present:
	Evidence of wear facets: yes no
	Evidence of lateral interferences:

Page 12

CLINICAL EVALUATION CRITERIA

Gingival Index

Gingival score (visual) for gingival area nearest to the crown margin; evaluate without disclosing. (Gingival scores will be based upon the standard Loe & Silness Index, 1963)

score 0 = normal gingiva

score 1 = mild inflammation - slight change in color, slight edema, no bleeding

score 2 = moderate inflammation - redness, edema and glazing, bleeding on probing

score 3 = severe inflammation - marked redness and edema, ulceration, spontaneous bleeding

Plaque Index

Plaque score (visual) for facial gingival area nearest to the crown margin; evaluate without disclosing. (Plaque scores will be based upon the standard Silness & Loe Index, 1964)

score 0 = no plaque detectable in the gingival area

score 1 = plaque recognized only by running tip of probe across tooth surface at gingival crest

score 2 = moderate accumulation of plaque visible along gingival margin and adjacent tooth

score 3 = abundance of plaque visible along gingival margin and adjacent tooth

score 3 = abundance of plaque visible along gingival margin and adjacent tooth	
Color Match (with control tooth, indirect lighting, without magnification) Tooth and restoration have an ideal color match; can distinguish restoration with some difficulty Readily perceptible mismatch in color; general match Obvious mismatch in color between tooth and restoration; unacceptable for cementation	Rating Alpha Bravo Charlie
Margin Adaptation (margin integrity)	
No visible evidence of crevice formation along cavosurface margin	
explorer does not catch when drawn across the margin	Alpha-1
No visible evidence of crevice formation along cavosurface margin	
Margin is detectable along less than 50% of cavosurface margin; and less than 1 mm in depth	Alpha-2
No visible evidence of crevice formation along cavosurface margin	
Margin is detectable along more than 50% of cavosurface margin; and less than 1 mm in depth	Alpha-3
Evidence of crevice formation (penetrable) along less than 50% of the cavosurface margin;	Bravo-1
greater than 1 mm in depth Evidence of crevice formation (penetrable) along greater than 50% of the cavosurface margin;	Dravo-1
greater than 1 mm in depth	Bravo-2
Evidence of crevice formation exposing dentin to the axial or pulpal floor	Charlie
Evidence of crevice formation exposing dentili to the axial of pulpar floor	Charne
Margin Discoloration (evaluated with tooth dry)	
No evidence of margin discoloration	Alpha
Surface stain along less than 50% of exposed margin	Bravo-1
Surface stain along greater than 50% of exposed margin	Bravo-2
Penetrating discoloration of exposed margin	Charlie
Surface Finish (surface of the restoration as viewed under magnification)	
Smooth, highly polished to finely granular	Alpha
Gritty, moderate rough but uniform texture	Bravo

Smooth, highly polished to finely granular	Alpha
Gritty, moderate rough but uniform texture	Bravo
Rough or pitted, visible evidence of significant pits and voids	Charlie
Evidence of surface crazing with no loss of ceramic or mobile pieces	Delta

Caries

No evidence of caries	Alpha
Evidence of recurrent caries at crown margin; repairable without compromise to crown	Bravo
Evidence of recurrent caries at crown margin; not repairable, crown requires replacement	Charlie

Clinical Evaluation of Chairside CAI	D/CAM Lithium Disilicate FPDs
Protocol 01	23 May 2022

Page 13

Abutment Fracture

No evidence of abutment crown fracture	Alpha
Evidence of restoration fracture with no missing piece or mobility in the pieces	Bravo
Evidence of restoration fracture with a missing piece considered polishable or repairable	Charlie
Fracture of the restoration requiring replacement	Delta

Connector Fracture

No evidence of connector fracture	Alpha
Evidence of connector fracture with no missing piece or mobility in the pieces	Bravo
Evidence of connector fracture with a missing piece considered polishable or repairable	Charlie
Fracture of the connector requiring replacement	Delta

Proximal Contact

Firm resistance to passage of floss with ideal breadth of contact area	Alpha
Light resistance to passage of floss or notable variance in breadth of contact area;	Bravo
shim stock will pass through contact	
	C1 11

Contact visibly open with passage of one thickness of articulating paper (blue)

Charlie

Pontic Fracture

No evidence of pontic fracture	Alpha
Evidence of pontic fracture without loss of material	Bravo
Pontic fracture with loss of material but repairable or does not require replacement	Charlie
Complete pontic fracture requiring replacement of the crown	Delta

Sensitivity

No sensitivity is experienced at any time	Alpha
Slight sensitivity is experienced occasionally but is not uncomfortable	Bravo
Moderate sensitivity is experienced intermittently and is noticeably uncomfortable	Charlie
Severe discomfort is noted routinely with cold or pressure stimulation	Delta

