8.2 Clinical Evaluation

Two independent evaluators will examine all FPDs in the study. Clinical evaluations will be made at baseline (the appointment the FPD is cemented), six months, one year, two years, three years, and optionally at four years, and five years using written criteria based on modified USPHS criteria for margin discoloration, margin adaptation, proximal contact, recurrent caries, surface finish, connector fracture, and crown fracture (see Appendix for criteria description). Disagreements in evaluations will be discussed between the evaluators and a consensus judgment will be reached and recorded for every criteria. Gingival health adjacent to the abutments and control teeth will be evaluated with a Gingival Score (Loe & Silness Index, 1963) and a Plaque Score (Silness & Loe Index, 1964).

Intraoral digital color images at a 1:1.5 magnification will be taken to document preoperative, tooth preparation, and post-operative conditions. Facial and occlusal views of the tooth will be documented for both the pre-operative and post-operative conditions.

A postcementation quadrant impression will be made of the midfacial margin of each abutment and the opposing teeth in a polyvinyl siloxane material and casts will be poured in an enhanced stone. Casts will be made at the baseline, 6 months, 1 year, 2 year, and 3 year, and optionally at the 4 year, and 5 year recall visits. Bite-wing radiographs and periapical radiographs of each test tooth will be available preoperatively and at the two year and optionally at the five year recall.

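### On the Pontic Fracture scale, a fracture that requires replacement but is not complete falls outside Delta: it is graded Bravo if no material is lost and has no grade if material is lost

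*Combined protocol and SAP*

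**What the plan says.** The Pontic Fracture scale in the Appendix (Clinical Evaluation Criteria) has four grades:

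- Alpha: "No evidence of pontic fracture"
- Bravo: "Evidence of pontic fracture without loss of material"
- Charlie: "Pontic fracture with loss of material but repairable or does not require replacement"
- Delta: "Complete pontic fracture requiring replacement of the crown"

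The two sister scales end differently. Connector Delta is "Fracture of the connector requiring replacement" and abutment Delta is "Fracture of the restoration requiring replacement". Neither asks whether the break is complete. Connector Bravo is "Evidence of connector fracture with no missing piece or mobility in the pieces", and abutment Bravo carries the same two exclusions.

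Section 8.2 has two evaluators rate every FPD against written criteria and provides that "Disagreements in evaluations will be discussed between the evaluators and a consensus judgment will be reached and recorded for every criteria". Its list of criteria names connector and crown fracture but not pontic fracture, so the Appendix is the only place where pontic fracture is defined. Section 9 tests the change in rating from baseline with a Wilcoxon signed-rank test, one category at a time. It plans no failure count or survival analysis.

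**The concern.** A graded scale should give each possible finding exactly one grade, and its worst grade should capture every restoration that has to be replaced for that reason. The pontic scale does neither. Bravo turns on loss of material alone. Charlie turns on loss together with repairability or no need for replacement. Delta turns on completeness together with need for replacement. These conditions neither exclude one another nor cover every case, and all the trouble falls on fractures that require replacement.

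The aim of the trial is to describe clinical performance over time in 30 FPDs (Sections 5 and 7.3). The documents contain no separate definition of failure or survival, so the fracture ratings are the only coded record of a replacement-level fracture. If such a fracture is entered under the mildest fracture grade, or not entered, a report built from the ratings understates the worst outcome on this scale.

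A smaller matter in the same line is that Delta speaks of replacing the crown, whereas the study unit is a three-unit FPD (Section 7.1).

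**Working it through.** The plan gives no figure to reproduce. The check applies the grade texts literally.

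**Inputs.** The pontic, connector and abutment grade texts from the Appendix. A fracture that requires replacement is treated as not repairable.

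**Step 1: pontic fractures that require replacement.** Loss of material and completeness can each be yes or no, which gives four states.

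| Material lost | Complete | Bravo (no loss) | Charlie (loss, and repairable or no replacement) | Delta (complete and replacement) | Result |
|---|---|---|---|---|---|
| No | No | fits | no | no | Bravo only |
| No | Yes | fits | no | fits | Bravo and Delta |
| Yes | No | no | no | no | no grade |
| Yes | Yes | no | no | fits | Delta only |

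**Step 2: pontic fractures that do not require replacement.** Without loss they are Bravo; with loss they are Charlie. Each gets exactly one grade, whether or not the break is complete.

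**Step 3: connector and abutment scales.** These turn on missing pieces and mobile pieces, so their four replacement-level states are missing (yes/no) by mobile (yes/no). All four satisfy Delta. The state with nothing missing and nothing mobile also satisfies Bravo.

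**Step 4: compare on the same test.**

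| Replacement-level states | Pontic | Connector and abutment |
|---|---|---|
| Delta is available | 2 of 4 | 4 of 4 |
| Delta is the only grade | 1 of 4 | 3 of 4 |

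The first row is the defect specific to the pontic scale. The second row shows that overlap exists on all three scales. The second axis differs between scales, and these are counts of logical states, not of patients.

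**Step 5: size for a description.** One FPD of 30 is 1/30 = 3.3 percentage points. If one replacement-level fracture is recorded as Bravo, a Delta proportion of 1/30 (3.3%, exact 95% CI 0.1% to 17.2%) becomes 0/30 (upper limit 11.6%).

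**Step 6: effect on the Section 9 test.** Assume every pontic is Alpha at cementation (the documents do not say so) and that unchanged FPDs drop out of the test. Every change then has the same sign, and with k changed FPDs the exact two-sided p is 2 × (1/2)^k = 2^(1−k). The size of each change does not enter, so recording Bravo (one grade down) or Delta (three grades down) gives the same p. A fracture left ungraded lowers k by one and doubles p. As an illustration, k = 6 gives 2^(−5) = 0.031 and k = 5 gives 2^(−4) = 0.063.

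**The case against.** The strongest reply is that sensible evaluators would not be misled. The scale is ordered, and Charlie's reference to replacement suggests that replacement is the boundary with Delta. Two evaluators must also reach and record a consensus on every criterion, so a blank rating is unlikely. This has force in practice. But consensus settles disagreement between people. It does not say which grade applies when two fit or none does, and Section 8.2 promises written criteria. If complete was meant only as another way of saying that replacement is needed, the gap closes and the overlap remains; the documents do not say so.

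Four stronger readings are tempting and should be set aside.

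- A reader might infer that the connector and abutment scales are sound and only the pontic scale is ambiguous. They are not free of overlap (Step 3). They also leave a fracture with mobile but not missing pieces, not requiring replacement, without a grade.
- A reader might infer that the signed-rank results are biased. Between Bravo and Delta the exact p does not move under the assumption in Step 6; only a missing rating could move it.
- A reader might infer a proven bias in favour of the material. Only one of the four states is forced to Bravo. One more may be graded either way, one has no grade, and no replacement proportion is planned in Section 9.
- A reader might infer that pontic fracture is a leading mode of failure here. The documents give no rate, and only the connectors have a minimum size (Section 7.4).

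It is also fair to say that Delta is not uniform across the Appendix: Surface Finish Delta is crazing without loss, and replacement-level caries is Charlie. Matching letters across scales is therefore not the argument. The argument is that the pontic scale does not, on its own terms, grade every replacement-level fracture.

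**Conclusion.** The point holds as a defect in a measurement definition. Of the four kinds of replacement-level pontic fracture, two cannot be graded Delta as written (one is Bravo, one has no grade), a third fits Delta and Bravo equally, and only the complete fracture with lost material is unambiguous. The consequence is for the recorded ratings and for any account of replacement-level fractures, at 3.3 percentage points per FPD. The planned signed-rank test is affected only if a failure goes ungraded.

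This rests on a literal reading of the grades, on complete being a separate condition from replacement, and on treating a fracture that requires replacement as not repairable. How often such fractures occur cannot be judged from the documents, so the expected effect may be small. The correction is worth making because it costs very little and the trial has only 30 FPDs.

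**What to change.** Change the Appendix and the matching CRF lines as follows:

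- **Delta:** *Pontic fracture requiring replacement of the FPD*, whether or not it is complete and whether or not material is lost.
- **Bravo:** keep the present text and add *and not requiring replacement*.
- **Charlie:** keep for loss of material not requiring replacement.
- **All three fracture scales:** state that the worst applicable grade is recorded. This also settles the Bravo/Delta overlap on the connector and abutment scales.

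With these changes all four replacement-level pontic states become Delta, and the rest divide into Bravo (no loss) and Charlie (loss) with no gap or overlap.

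Do not copy the connector scale's mobility condition into pontic Bravo. A fracture with mobile but not missing pieces and no need for replacement is plainly Bravo now, and the copied wording would create a gap or overlap for it.

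The cost is a few lines of wording, with no extra visits, staff or procedures. The downside is that a few pontic fractures may be graded worse than under the current wording. If any pontic fractures have already been rated, those ratings should be checked against the revised text.
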